Study Subjects: We will recruit 15 otherwise healthy subjects using intramural and local extramural advertising after approval from the Mayo Clinic Institutional Review Board. Individuals who express interest in participating will be invited for a screening visit. Individuals with a BMI < 19 or > 40 kg/m² will be excluded from the study to avoid potential confounding effects that may result from extreme leanness or from obesity. Subjects will have no known systemic illness, taking any medication that could affect glucose metabolism and no history of upper gastrointestinal surgery.

Exclusion Criteria: Subjects < 18 years of age or > 60 years of age will not be studied to minimize the potential confounding effects of age on glucagon and insulin action. The subjects will not be taking medications that affect glucose metabolism (to be determined by PI) and have no history of chronic illness or upper gastrointestinal surgery. We are seeking to recruit subjects who do not have diabetes (fasting glucose <100mg/dL).

Screening Visit: To ensure subjects are healthy, following written, informed consent, subjects will undergo a history and physical examination, vital signs, height, weight, blood collection (after an 8 hour fast) for complete blood count, creatinine, sodium, potassium, fasting glucose and urine collection for point of care pregnancy testing for females able to become pregnant. Subjects will be instructed to consume a weight maintenance diet (55% carbohydrate, 30% fat and 15% protein, caffeine free) for at least 3 days prior to each study visit. **Body Composition:** Body composition will be measured prior to participation using dual-energy X-ray absorptiometry (iDXA scanner; GE, Wauwatosa, WI).

Experimental Design: Volunteers will participate in a total of 2 protocols. The overnight studies will be performed at least a week apart in random order.

cannula will be inserted retrogradely into a vein of the contra-lateral dorsum of the hand. This will be placed in a heated Plexiglas box maintained at around 120°F to allow sampling of arterialized venous blood. At approximately 0600 (-180 min), a primed, (10 μ Ci prime, 0.1 μ Ci/min continuous) infusion containing trace amounts of glucose labeled with [3-³H] glucose will be started and continued till 0900 (0 min).

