At 0900 (0 min), the infusion will be varied so as to mimic the anticipated pattern of fall of EGP. In addition, glucose also labeled with [3-³H] glucose will be infused so as to maintain glucose concentrations at ~ 95mg/dL. Peripheral venous glucose concentrations will be measured every 10 minutes to allow the infusion rate of glucose to be adjusted as necessary.

Simultaneously, an infusion of somatostatin (60ng/kg/min) will be started at time 0 to inhibit endogenous islet secretion and therefore ensure identical portal insulin concentrations on the two study days(8). Insulin will be infused at a constant rate known to produce ~ 50% suppression of EGP (0.4mU/Kg/min).

From 0900 (0 min) to 1030 (90 min) no glucagon will be infused. Subsequently, a glucagon infusion will commence (91 – 180 min) at 0.35 ng/Kg/min and then increase to 0.70 ng/Kg/min (181- 270 min), a rate which will be maintained till the end of the study (1330).

Study B (0.8mU/Kg/min): Approximately 1-2 weeks after the first study visit, subjects will be asked to return to the CRTU. This study visit will be similar to Study A. However, insulin will be infused at 0.8mU/Kg/min 0 to 270 minutes.

Analytical Techniques: All blood will be immediately placed on ice, centrifuged at 4°C, separated and stored at -80°C until assay. Glucose will be measured using a Yellow Springs glucose analyzer. Glucagon will be measured using an ELISA (Mercodia, Winston-Salem, NC). C-peptide will be measured using EMD Millipore (Billerica, MA) reagents. Insulin will be measured using a chemiluminescence assay with reagents obtained from Beckman (Access Assay, Beckman, Chaska, MN). [3-³H] glucose specific activity will be measured by liquid scintillation counting following deproteinization(14). Endogenous glucose production (EGP) and glucose disposal (Rd) will be measured as before(9; 15).

Study A (Insulin 0.4mU/Kg/min):

Subjects will be admitted to the CRTU at approximately 1700 on the day prior to study. They will then consume a standard 10kcal/kg meal (55% carbohydrate, 30% fat, 15% protein, caffeine free) and fast overnight. Blood will then be sampled for baseline enrichment and ²H₂O (1.67g/kg of body water) will be given in 3 divided doses at 2200, 2400 and 0200 (13). The following morning (approximately 0530), a forearm vein will be cannulated to allow infusions to be performed. In addition, a

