Calculations: Glucose appearance and disappearance will be calculated using the steady-state equations of Steele et al., in which the actual tracer infusion rate for each interval is used in the calculation. The volume of distribution of glucose will be assumed to equal 200 ml/kg, and the pool correction factor assumed to be 0.65(16). Endogenous glucose production will be determined by subtracting the glucose infusion rate from the tracer-determined rate of glucose appearance(9). All rates of infusion and turnover will expressed per Kg/lean body mass.

Mean \pm SD	Detectable difference (0.4 vs. 0.8 insulin)	Detectable difference within each sub-group
Nadir EGP ($\mu\text{mol}/\text{kg}/\text{min}$)	3.9 ± 1.1	0.4 (10%)
AUC EGP ($\mu\text{mol}/\text{kg}$ per 5hr)	2816 ± 182	67 (2%)

Table 1: Pooled Means \pm SD used to estimate power. (Data from Ref. 1)

Statistical Analysis: A paired, two way student t-test (parametric) or a Wilcoxon matched-pairs

signed rank test (non-parametric) will be used to examine changes of EGP at the various time points of each study day. Differences between the 3 glucagon infusion rates will be assessed using a repeated-measures ANOVA which assumes the absence of a Gaussian distribution (Friedman test). Subsequently, in the presence of significant between group differences ($p < 0.05$), a *post-hoc* Student's t-test will used to examine differences between the 3 infusion rates of glucagon. If values are not normally distributed, a Dunn's test will be used instead.

Power calculation: Assuming similar variation to that previously observed(1), 60 subjects would provide approximately 80% power (at a 2-sided 0.05 α level), to detect small, biologically significant, differences in peak glucose, glucose area above basal and EGP in the presence and absence of glucagon suppression (Table 1, Col 3) as would 20 per subgroup (Table 1, Col 4).

D. Interpretation

We will accept our 1° hypothesis if endogenous glucose production (EGP) is higher during the 0.4 vs. the 0.8 study day. This would imply that despite rising glucagon concentrations higher insulin concentrations can still restrain EGP. It also will allow us to quantify the fold changes in EGP at low or high insulin concentrations.

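### The only power statement is for 60 subjects (or 20 per subgroup), but the trial recruits 15 with no subgroups; on Table 1's own inputs, 15 subjects have about 26% power at the tabulated differences

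*Combined protocol and SAP*

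**What the plan says.** Section C, Study Subjects: "We will recruit 15 otherwise healthy subjects". Under Experimental Design every volunteer completes both study days in random order. No subgroups are defined.

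Section C, Power calculation, is the only sample-size justification. It states that "60 subjects would provide approximately 80% power" at a two-sided 0.05 level, and adds "as would 20 per subgroup (Table 1, Col 4"). The targets are "differences in peak glucose, glucose area above basal and EGP in the presence and absence of glucagon suppression". The paragraph describes the differences it can detect as small but biologically meaningful.

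Table 1 gives nadir EGP as 3.9 ± 1.1 µmol/kg/min with a detectable difference of 0.4 (10%), and AUC EGP as 2816 ± 182 µmol/kg per 5 hours with 67 (2%). Its caption describes the entries as pooled means and "SD used to estimate power. (Data from Ref. 1"). It does not say whether these are between-subject SDs or SDs of a within-subject difference.

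The design that the table should support is different. Glucose is infused "so as to maintain glucose concentrations at ~ 95mg/dL". The two days differ in insulin rate (0.4 against 0.8 mU/kg/min), and on the second "insulin will be infused at 0.8mU/Kg/min 0 to 270 minutes". For the analysis, "All rates of infusion and turnover will expressed per Kg/lean body mass".

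**The concern.** The stated power belongs to a study four times this size (60/15 = 4). Sixty subjects at 20 per subgroup implies three subgroups, and this trial has none. Section B describes a prior experiment with three insulin profiles, so the text may have come from there; that is an inference, and nothing below depends on it.

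The content does not fit either:

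- Peak glucose and glucose area above basal are not meaningful targets when glucose is clamped.
- Glucagon follows the same steps on both days, so there is no between-day contrast in glucagon suppression.
- The AUC row covers 5 hours, whereas the infusions run 270 minutes (4.5 hours).
- Table 1 is per kg, whereas the analysis is per kg of lean body mass.

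A reader therefore cannot tell what difference the trial can detect. This matters for the 1° hypothesis, and more for the 2° hypothesis, which section D accepts if percent suppression does not differ between days. When finding no difference counts as success, the detectable difference decides what that success means, and the percent-of-fasting endpoint has no row in Table 1.

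**Working it through.** **Inputs.** Table 1: SD 1.1 and difference 0.4 (nadir); SD 182 and difference 67 (AUC). Power calculation: two-sided 0.05, about 80% power, n = 60 or 20. Study Subjects: n = 15. Statistical Analysis: paired t-test, with the Wilcoxon signed-rank test as the alternative.

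**Formula.** For a paired t-test, power = P(|T| > t at 0.975 with n − 1 df), where T is noncentral t with noncentrality (Δ/SD_d) × √n, and SD_d is the SD of the within-subject difference.

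**Step 1: reproduce the plan's figure.** Take the tabulated SD as SD_d.

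- Nadir, n = 60: 0.4/1.1 = 0.364; × √60 = 2.82; power 79.1%.
- AUC, n = 60: 67/182 = 0.368; × √60 = 2.85; power 80.1%.
- In reverse, 80% power at n = 60 needs 0.368 × SD_d, which gives 0.404 and 66.9, against the tabulated 0.4 and 67.

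Other readings fail. Two independent groups of 60 would detect 0.567 and 93.9; groups of 30, 0.809 and 133.9; groups of 20, 1.00 and 165.5. A one-sided paired test would give 87–88% power. Twenty paired subjects would detect 0.660 × SD_d = 0.73 and 120.

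The table is broken in the text available to me and shows only one column of differences. Assigning 0.4 and 67 to the 0.4-versus-0.8 insulin column is inferred from this match and from the text that ties that column to 60 subjects.

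**Step 2: same formula, n = 15.**

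| | Power at tabulated difference | Detectable at 80% power (0.778 × SD_d) | Share of mean |
|---|---|---|---|
| Nadir EGP | 25.9% | 0.856 | 0.856/3.9 = 22% |
| AUC EGP, 5 h | 26.5% | 141.6 | 141.6/2816 = 5.0% |

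The ratio of detectable differences, n = 15 to n = 60, is 2.12.

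**Step 3: if the SDs are between-subject.** Then SD_d = SD × √(2(1 − ρ)), with ρ the within-subject correlation. At n = 15:

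| ρ | Power for 0.4 | Detectable nadir | Detectable 5-h AUC |
|---|---|---|---|
| 0 | 15% | 1.21 | 200 |
| 0.5 | 26% | 0.86 | 142 |
| 0.75 | 46% | 0.61 | 100 |
| 0.9 | 83% | 0.38 | 63 |

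Fifteen subjects reach 80% power for 0.4 only at ρ of about 0.89. At ρ = 0.9, however, 60 subjects would have power near 100% for 0.4, not the stated 80%. Of the correlations tried (0, 0.25, 0.5, 0.75, 0.9), only 0.5, where SD_d equals the tabulated SD, also gives about 80% at n = 60.

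**Step 4: larger effects.** With n = 15 and SD_d = 1.1, power is 50% for 0.6, 75% for 0.8, 90% for 1.0 (1.0/3.9 = 26%) and 97% for 1.17 (30%). For 1.0 under the between-subject reading, power is 64% at ρ = 0 and over 99% at ρ = 0.75.

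**The case against.** **The 26% is conditional.** The protocol never says that the SDs are SDs of paired differences, and the source study cannot be seen. Under the between-subject reading, power for 0.4 runs from 15% to 83%. This stands for the absolute figures. It does not rescue the paragraph: under a paired t-test, any difference with 80% power at n = 60 equals 0.368 × SD_d, and 15 subjects have about 26% power for it whatever SD_d is. No single SD makes both 60 and 15 subjects give 80%.

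**The subgroup column may be the fairer benchmark.** The protocol also presents the differences detectable with 20 per subgroup as small. If those were 0.73 and 120, 15 subjects would have about 66% power, and the detectable difference would be 0.778/0.660 = 1.18 times as large, not 2.1. A correlation of about 0.64 would then suffice for 0.73. This is fair, but those values are not visible, the column is headed as a within-subgroup comparison, and there are no subgroups. It softens any statement that a correlation near 0.9 is required; the mismatch remains.

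**Nothing shows that the trial is too small.** This stands. The documents do not give the expected difference between insulin rates, and power is good for differences of about 1 µmol/kg/min on the same SD. Table 1's arithmetic is also right for 60 subjects.

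**The recomputed figures transfer imperfectly.** This stands too. They inherit a 5-hour SD and per-kg units, and neither nadir nor AUC is named as the primary endpoint.

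**Conclusion.** The concern holds. The protocol's only power statement describes 60 subjects, subgroups that do not exist, and comparisons this trial does not make. It therefore does not support sensitivity to small differences with 15 subjects.

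The factor of about 2.1, and the fall from 80% to about 26% power, follow from replacing 60 paired subjects by 15. The absolute values of 0.86 and 142 rest on Table 1's SDs being SDs of the paired difference, which is the reading that reproduces the table. None of these figures applies to percent-of-fasting EGP, for which the documents give no SD. The finding concerns the justification and what readers can infer from it; it is not evidence that the primary comparison is underpowered for a larger effect.

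**What to change.** Rewrite the Power calculation paragraph and Table 1 for 15 subjects, paired, two-sided 0.05, where 80% power detects 0.78 × the SD of the within-subject between-day difference:

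1. State which SD is used, its source, and whether it is between-subject or the SD of a difference.
2. If Table 1's SDs are kept, give 0.86 (nadir) and 142 (5-hour AUC) explicitly as results of that assumption, with the range over correlations 0 to 0.9: 1.21 to 0.38 and 200 to 63. The AUC figures are a stopgap until item 3 is done.
3. Replace the AUC row with one based on a 270-minute SD, and express both rows per kg of lean body mass. The documents do not contain these SDs, so they must be found or declared as assumptions.
4. Add a detectable between-day difference for percent-of-fasting EGP with its assumed SD. For illustration, SDs of the difference of 10, 20 and 30 percentage points give 7.8, 15.6 and 23.3 points at a single time point.
5. Delete the wording on 60 subjects, 20 per subgroup, peak glucose, glucose area and glucagon suppression.

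The cost is protocol wording plus the work of finding or assuming a within-subject SD. No extra subjects are needed. The stated sensitivity will look less favourable.

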Title

**The Effect of the Interaction of Glucagon and Insulin on Endogenous
Glucose Production in Humans**

Protocol Number: 20-001570

Principal Investigator: [name]

IND Sponsor: [name], # 116569 (Somatostatin)

Funded by: Intramural Funds

Version Number: 2

January 13, 2021

NCT: 04461015

Specific Aim: Determine the relative contribution of changes in insulin and glucagon concentration on endogenous glucose production in nondiabetic subjects.

1° Hypothesis: Hyperinsulinemia restrains the effect of rising glucagon concentrations on endogenous glucose production

2° Hypothesis: The % change in endogenous glucose production in response to rising glucagon concentrations is unchanged by hyperinsulinemia

Rationale: The experimental design we propose will enable the dissection of the relative contribution of insulin and glucagon concentrations to endogenous glucose production. Acquisition of this data will allow us to develop a model of insulin and glucagon contributions to postprandial glucose metabolism (1; 2).

A. Significance

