To test our 2° hypothesis we will express EGP at 80, 180 and 270 minutes as a percentage of fasting EGP (0 min). The relative changes with increments in glucagon will demonstrate whether the relationship is linear or asymptotic. Comparison of the two study days will enable us to determine the effect of insulin on this relationship. We will accept our 2° hypothesis if % suppression at the 80, 180 and 270 minute time points does not differ between study days.

We will calculate changes in nadir and integrated rates of EGP, as previously described(17-20), to compare suppression between the two study days. We will also undertake exploratory analysis of the rates of glucose disappearance (Rd) to determine if differences in glucagon concentrations affect Rd as well as EGP.

Limitations / Precautions/ Additional or Alternative Analyses:

- Inhibition of glucagon secretion by somatostatin lowers portal concentrations. In the case of glucagon, an infusion that maintains peripheral concentrations of glucagon constant likely will result in a ~10% decrease in portal glucagon concentrations(21-23). However, in the current experimental design, the portal glucagon concentrations on the two study days will not differ.

E. Human Subjects

Detailed Description: Suitable volunteers will be asked to visit the CRTU on a total of 3 occasions, including screening. During the first or screening visit they will meet with a member of the study team and undergo a history and physical examination to ensure that they fulfill entry criteria. If eligible, they will be asked to undergo determination of body composition. After an overnight fast, a cannula will be placed to allow IV infusion. Infusions will be started on the study days. In addition a retrograde hand vein for blood draws will be placed. This hand will be placed in a Perspex hot-box heated to about 120 °F. Blood will be sampled several times (via the retrograde hand vein) to obtain arterialized venous samples.

Population: Subjects will be recruited using intramural and local extramural advertising after approval from the Mayo Clinic Institutional Review Board. The racial composition of the county is outlined in the table below (%) using data from the 2000 population census. No children or prisoners will be recruited.

	American Indian or Alaskan Native	Asian or Pacific Islander	Black, not of Hispanic Origin	Hispanic	White, not of Hispanic Origin	Other	Total
Female	0.15	2.8	1.8	1.5	43.8	0	51.5

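### The primary hypothesis concerns insulin's effect on the glucagon response, but its acceptance rule tests only insulin's effect on the level of EGP

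*Combined protocol and SAP*

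**What the plan says.** The opening page states the 1° hypothesis as "Hyperinsulinemia restrains the effect of rising glucagon concentrations on endogenous glucose production". The trial's title also names the interaction of the two hormones.

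Section C gives the design. Each subject has two study days, with insulin at 0.4 and 0.8 mU/kg/min. The 0.4 rate is described as known to suppress EGP by about 50%. "From 0900 (0 min) to 1030 (90 min) no glucagon will be infused"; glucagon then runs at 0.35 ng/kg/min (91–180 min) and 0.70 ng/kg/min (181–270 min). Study B differs from Study A only in the insulin rate.

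Section D gives the decision rule: "We will accept our 1° hypothesis if endogenous glucose production (EGP) is higher during the 0.4 vs. the 0.8 study day". It adds: "This would imply that despite rising glucagon concentrations higher insulin concentrations can still restrain EGP".

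The Statistical Analysis paragraph has two elements: a paired t-test or Wilcoxon test of EGP at the various time points, and a Friedman test across the three glucagon rates.

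For the 2° hypothesis, section D expresses EGP at 80, 180 and 270 min as a percentage of the fasting value at 0 min and says: "Comparison of the two study days will enable us to determine the effect of insulin on this relationship". Its rule is: "We will accept our 2° hypothesis if % suppression at the 80, 180 and 270 minute time points does not differ between study days".

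**The concern.** The hypothesis is about how much EGP rises when glucagon rises, and whether that rise is smaller under more insulin. The rule asks only whether EGP is lower under more insulin, which the plan already expects of insulin without any glucagon. Nothing in the rule subtracts the gap that exists before glucagon starts.

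The sentence also names no time point, summary measure or test. The trial could therefore report that insulin restrains glucagon's effect when the data show only that insulin lowers EGP, or when the glucagon response is larger on the high-insulin day.

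**Working it through.** **1. The logic, with illustrative EGP values (assumed, µmol/kg/min) at glucagon 0 / 0.35 / 0.70**

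| Case | 0.4 day | 0.8 day | Glucagon rise, 0.4 vs 0.8 day | Is EGP higher on the 0.4 day? |
|---|---|---|---|---|
| No interaction | 6 / 8 / 10 | 4 / 6 / 8 | 4 vs 4 | Yes, at every step |
| Opposite interaction | 6 / 7 / 8 | 3 / 5 / 7 | 2 vs 4 | Yes, at every step |

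The rule accepts the hypothesis in both cases, although the hypothesis is false in both.

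**2. Whether other text repairs the rule**

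- The paired test at time points compares levels or changes, with no glucagon-by-insulin contrast named. The Friedman test has one factor, the glucagon rate.
- The 2° comparison is the nearest thing, but it does not feed the 1° rule. It includes the glucagon-free 80 min value and divides by EGP at 0 min. If fasting EGP is the same value F on both days, the difference in percentages is 100 × (EGP on the 0.4 day − EGP on the 0.8 day)/F. Insulin's own effect therefore stays in it.
- The planned nadir and integrated EGP comparisons are between-day comparisons of level or suppression, not of the glucagon-induced change.

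**3. Inputs for the size**

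- n = 15 (section C, Study Subjects).
- SD 1.1 for nadir EGP (Table 1), read as the SD of the paired difference. Check: at n = 60, 80% power and two-sided 0.05, the noncentral t gives a standardised difference of 0.368. Then 0.368 × 1.1 = 0.40 and 0.368 × 182 = 66.9, matching Table 1's 0.4 and 67.
- If 1.1 is instead the SD on one day and the days are uncorrelated, the paired SD is 1.1 × √2 = 1.56.
- Assumed: a paired t-test at 270 min and between-day shifts of 0.4 to 1.3 µmol/kg/min.

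**4. Zero interaction**

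The chance of meeting the rule with significance is P(T > 2.145), where T is noncentral t on 14 df with noncentrality √15 × shift/SD. For a shift of 1.0 and SD 1.1, that is 3.873 × 1.0/1.1 = 3.52, giving 0.905.

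| Shift | 0.4 | 0.8 | 1.0 | 1.3 |
|---|---|---|---|---|
| SD 1.1 | 26% | 75% | 91% | 99% |
| SD 1.56 | 15% | 46% | 64% | 85% |

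If higher is read numerically, without a test, the smallest shift already meets the rule in Φ(√15 × 0.4/1.1) = Φ(1.41) = 92% of trials, or Φ(1.00) = 84% at SD 1.56. A two-sided 0.05 test of the between-day difference in change from 80 min is positive in the hypothesised direction in about 2.5%, which is one tail of alpha.

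**5. Opposite interaction**

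Let the gap narrow from 1.5 at 80 min to 1.0 at 270 min, so that glucagon raises EGP by 0.5 more on the 0.8 day. The gap at 270 min is still 1.0, so the rule is met in about 90% (SD 1.1) or 64% (SD 1.56). The change contrast supports restraint in at most 0.27%. That maximum is at SD 1.56 with zero correlation between the 80 and 270 min differences.

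**6. Precision of the matching contrast**

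Its SD is SD × √(2(1 − ρ)), where ρ is the correlation between the paired differences at 80 and 270 min. At n = 15 the difference detectable with 80% power is 0.778 times that SD.

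| ρ | 0.8 | 0.5 | 0 |
|---|---|---|---|
| SD 1.1 | 0.54 | 0.86 | 1.21 |
| SD 1.56 | 0.77 | 1.21 | 1.71 |

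The level comparison detects 0.86 (SD 1.1) or 1.21 (SD 1.56), so the contrast is noisier when ρ is below 0.5.

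**The case against.** The strongest reply is that the protocol explains itself. The sentence after the rule claims only that more insulin still lowers EGP despite rising glucagon, and the rule does address that. Read with the 2° hypothesis, a coherent pair is possible: insulin lowers the level, and the proportional glucagon response is preserved. The defect would then be one loosely worded hypothesis line. This stands as a possible reading and as a route to a fix. It does not remove the mismatch, and item 5 of the Preliminary Data (a more marked glucagon effect at lower insulin) points to the interaction reading.

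The plan also names between-day summaries elsewhere: nadir and integrated EGP in section D, and Table 1's column for the 0.4 versus 0.8 comparison. Section D further mentions quantifying fold changes in EGP at low and high insulin. None of these is tied to the rule as a test of the glucagon response.

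The percentages rest on assumed shifts and on a nadir SD applied at 270 min. That SD is tabulated per kg, whereas rates are to be expressed per kg lean body mass. This is fair. With the AUC row instead (SD 182, a 0.4 shift sustained for 270 to 300 min, so 108 to 120), the 26% becomes 57% to 66%. The choice of summary matters, but here it makes the problem larger. The opposite-direction example is a test of the rule, not a forecast.

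Finally, an absolute contrast depends on scale. If glucagon multiplies EGP by the same factor on both days, the absolute rise is smaller where EGP is lower. That is true and must be stated. Because the 2° hypothesis already takes the percentage scale, the absolute scale is the coherent one for the 1° test.

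**Conclusion.** The concern holds. The rule for the primary hypothesis tests insulin's main effect on EGP, and no other part of the plan supplies the missing interaction test. With no interaction, the rule would be met with significance in 15% to 99% of trials over the assumed shifts and SDs, against about 2.5% for the matching contrast. Those figures depend on the assumed test, time point, shifts and SD. The logical failure depends on none of them. Because this rule carries the trial's main conclusion, either it or the hypothesis must be changed before the data are analysed.

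**What to change.** Replace the 1° rule with wording such as:

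> For each subject and day the glucagon response is EGP(270) − EGP(80). The 1° hypothesis is accepted if this response is significantly smaller on the 0.8 than on the 0.4 day (paired t-test, or Wilcoxon signed-rank if not normal, two-sided 0.05). EGP(180) − EGP(80) is supportive. The between-day difference in EGP level is reported descriptively as the effect of insulin.

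A linear mixed model with insulin day, glucagon step, their interaction, period and subject is an alternative, though not an equivalent.

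State two limits with it:

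- **Scale.** The 1° test is absolute. Report the same contrast as a percentage or ratio for the 2° hypothesis. If glucagon multiplies EGP by an assumed 1.5 to 2 on both days, a gap g at 80 min gives a contrast of (factor − 1) × g. This is significant in 5% to 100% of trials (g 0.4 to 1.3, ρ 0 to 0.8, SD 1.1 to 1.56). A positive 1° test would therefore not contradict the 2° hypothesis.
- **Time order.** Glucagon steps run in the same order on both days, and there is no full-length glucagon-free day. The contrast therefore also carries any continuing insulin effect after 80 min.

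If only the weaker claim is intended, reword the 1° hypothesis to say that higher insulin still lowers EGP despite rising glucagon, and do not conclude that insulin restrains glucagon's effect.

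The cost is new analysis wording and a power calculation for the contrast at n = 15. No samples or visits are added. The price may be lower power: at SD 1.1 the detectable differences of 0.54 to 1.21 are 14% to 31% of Table 1's nadir mean of 3.9.

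### The acceptance rule for the secondary hypothesis compares EGP as a percentage of fasting EGP, so it keeps insulin's own suppression and tends to reject a true hypothesis about the response to glucagon

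*Combined protocol and SAP*

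**What the plan says.** The secondary hypothesis, stated with the Specific Aim, reads: "The % change in endogenous glucose production in response to rising glucagon concentrations is unchanged by hyperinsulinemia". It is a claim about the relative response to glucagon.

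Section D (Interpretation) gives the measure: "we will express EGP at 80, 180 and 270 minutes as a percentage of fasting EGP (0 min". The decision rule follows in the same paragraph: "We will accept our 2° hypothesis if % suppression at the 80, 180 and 270 minute time points does not differ between study days".

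Section C (Research Design and Methods) starts insulin and somatostatin at time 0 and adds: "From 0900 (0 min) to 1030 (90 min) no glucagon will be infused". Glucagon then runs in two steps, from 91 and from 181 minutes. Insulin is 0.4 mU/kg/min on one day and 0.8 on the other, in random order, in 15 subjects.

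Section D also plans descriptions closer to the hypothesis: "The relative changes with increments in glucagon will demonstrate whether the relationship is linear or asymptotic", then "Comparison of the two study days will enable us to determine the effect of insulin on this relationship", and under the primary hypothesis "It also will allow us to quantify the fold changes in EGP at low or high insulin concentrations". The acceptance sentence uses none of these.

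**The concern.** The denominator is measured before insulin, somatostatin or glucagon has acted. Each percentage therefore combines suppression by that day's insulin rate with whatever glucagon does afterwards. Comparing the percentages between days tests the two together, whereas the hypothesis concerns only the second. At 80 minutes no glucagon has been infused, so that comparison is purely one insulin rate against the other. Even so, a difference there is enough to defeat acceptance.

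The rule also pulls against the primary one: "We will accept our 1° hypothesis if endogenous glucose production (EGP) is higher during the 0.4 vs. the 0.8 study day". Order is randomised, so expected fasting EGP is the same on both days. Higher EGP on the 0.4 day at a given time then means a higher percentage of fasting at that time. At matched times, the effect that satisfies the primary rule violates the secondary one, although the primary rule names no time point.

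At stake is the formal verdict on one of the study's two hypotheses. It could contradict the relative changes reported beside it.

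**Working it through.** **The plan's own power figure.** Section C claims about 80% power with 60 subjects. For nadir EGP (difference 0.4, SD 1.1), taking the SD as that of a paired difference: 0.4 × √60 / 1.1 − 1.96 = 0.857, which gives 80.4%. The figure reproduces. It does not concern the secondary rule, but it supports trying 1.1 as a paired SD.

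**Algebra.** Let p be EGP before glucagon as a fraction of fasting, and g(t) the glucagon multiplier, equal on both days because the secondary hypothesis is taken as true. The percentage of fasting is 100 × p × g(t), so the between-day gap is

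100 × (p₀.₄ − p₀.₈) × g(t).

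It is zero only if p₀.₄ = p₀.₈.

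**Example.** Assume g = 1, 1.25 and 1.5 at 80, 180 and 270 minutes, with p₀.₄ = 0.50. Section C gives about 50% suppression for the 0.4 rate but does not tie it to 80 minutes. Suppression at 0.8 is not stated, so two values are shown.

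| | 80 min | 180 min | 270 min | 270/80 |
|---|---|---|---|---|
| 0.4 day | 50 | 62.5 | 75 | 1.5 |
| 0.8 day, p = 0.45 | 45 | 56.25 | 67.5 | 1.5 |
| Gap | 5 | 6.25 | 7.5 | none |
| 0.8 day, p = 0.40 | 40 | 50 | 60 | 1.5 |
| Gap | 10 | 12.5 | 15 | none |

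The reverse error is also possible. A rise from 50% to 75% of fasting is +50%, and a rise from 40% to 75% is +87.5%, yet the 270-minute values agree.

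**How often the rule would reject a true hypothesis.** The model is the one above with n = 15 and 10,000–20,000 simulated trials per setting. The assumptions are paired SD 1.1–2.2, fasting EGP 8–14 (same units), fasting CV 0–10%, and within-day error correlation 0–0.5. Only the ratio of fasting EGP to paired SD matters, so the unresolved scale (per kg, or per kg lean mass) does not. The ratio runs from 8/2.2 = 3.6 to 14/1.1 = 12.7. The acceptance sentence names no test, so several readings are shown.

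| Reading of the rule | 0.8 day at 45% | 0.8 day at 40% |
|---|---|---|
| Any of three t-tests at 0.05 | 26–99% | 59–100% |
| 270-minute test alone | 15% to just over 90% | 44–100% |
| Three tests, Bonferroni | 12–95% | 37–100% |
| Joint Hotelling test | 10–97% | 28–100% |
| All three must differ | 0.2% to about 50% | 4–99% |

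At 35% of fasting, the any-of-three rate is 87–100%. With no added insulin effect it is 10–15%, which is multiplicity and not the denominator. The next three readings have a null rate of about 4–5% and show the same pattern, so multiplicity is not the cause.

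**Cross-checks.** At n = 15 a paired t-test has 80% power for 0.78 SD. A 10-point gap at 80 minutes is detected with 98, 73 or 44% power for a paired SD of 9, 14 or 20 points; for scale, 1.1/8 is 13.75 points. A separate model with log-scale errors and multipliers 1.2 and 1.4 puts the 0.8 day at 40% of fasting. At least one of the three times then differs in 97, 71 or 48% of trials for log-SD 0.15, 0.28 or 0.40. In that model, ratios to the 80-minute value reject a true hypothesis in about 5% of trials per time point.

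**The case against.** The strongest reply is that the same section already plans fold changes, relative changes with glucagon increments and the effect of insulin on that relationship, with 80 minutes as the zero-glucagon step. This stands as far as it goes: the response would be seen and no data are lost. The defect is confined to the acceptance sentence, but that sentence gives the verdict.

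The size is conditional. At a 5-point gap and high variability, most trials would not reject. That stands, though acceptance would then come from an insensitive test. Section C names a paired t-test or a Wilcoxon test for EGP at the various time points. The Wilcoxon test was not simulated, but the algebra does not depend on the test.

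The primary hypothesis could also hold with equal 80-minute EGP and a smaller glucagon rise on the 0.8 day. True, but then the secondary hypothesis is false. Where the secondary hypothesis is true, higher EGP on the 0.4 day implies higher EGP at 80 minutes.

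Finally, a rule based on the 80-minute value is vulnerable if insulin's effect is still developing then. This stands as a limit. With paired SD 1.1, suppose insulin alone lowers EGP to 0.95 (0.4 day) and 0.90 (0.8 day) of its 80-minute value. The replacement then rejects a true hypothesis in 11–26% of trials, and at 0.95 and 0.85 in 30–77%. In the first case the stated rule rejects in 83–100% when fasting EGP is free of error.

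**Conclusion.** The concern holds, with high confidence in the structure. The acceptance rule does not measure the quantity in the secondary hypothesis. It tends to reject a true hypothesis whenever the higher insulin rate adds suppression before glucagon starts. How often it would do so cannot be fixed from the documents, which do not give suppression on the 0.8 day, fasting EGP, the glucagon response or the paired SD. Under the ranges assumed here, an added suppression of 5 points already raises the error well above its reference rate on most readings, and 10 points makes rejection more likely than not under the any-of-three reading. The rule should be corrected before analysis. The primary hypothesis is not affected.

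**What to change.** Rewrite the acceptance sentence around each day's proportional change from its own 80-minute EGP:

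- Estimate the between-day contrast from day means: mean EGP(270)/mean EGP(80) on the 0.4 day minus the same ratio on the 0.8 day. Give a paired delta-method 95% confidence interval with t on 14 df. A repeated-measures log-link model with a day-by-glucagon-step interaction is an alternative.
- Name the 270-minute contrast as deciding and 180/80 as supportive, or adjust for two.
- Judge whether the response is unchanged from the interval, not from non-significance.
- Take the 80-minute comparison out of the rule and report it as the insulin contrast without glucagon infusion. Keep percentage of fasting as descriptive.
- Do not average per-subject ratios, which are biased upward on the 0.8 day when 80-minute EGP is low. Do not use per-subject log ratios if any EGP is near or below zero. Avoid a simple percentile bootstrap (coverage 90–93% at n = 15).

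With insulin's effect steady by 80 minutes, this contrast rejects a true hypothesis in about 4–5% of trials.

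The cost is one sentence and a short estimator definition, since all three time points are already planned. Two limits should be stated. First, precision: at paired SD 1.1 the half-width is about 12–29 points with the 0.8 day at 45% of fasting, 14–33 at 35% and 18–43 at 25%, and roughly double at SD 2.2. A halved response (25 points) would be significant in 27–99% of trials at SD 1.1 and 13–60% at SD 2.2, so a tight claim of no change may be out of reach. Second, drift: if insulin alone later takes EGP to fractions d₄ and d₈ of the 80-minute value, the contrast shifts by 150 × (d₄ − d₈) points. For 0.95 and 0.90 that is 150 × 0.05 = 7.5 points. Both days receive glucagon from 91 minutes, so the data cannot separate this.
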